3. STUDY DESIGN

STATISTICAL ANALYSIS PLAN

The design is a three-arm, parallel-assignment randomized controlled trial design to test the efficacy of ESTEEM with two comparison conditions—LGBTQ-affirmative community mental health treatment (CMHT) and brief voluntary HIV counseling and testing (VCT) only. The unit of randomization is the individual. The primary outcome is condomless anal sex in the absence of either PrEP or known undetectable viral load of HIV+ primary partners, measured with the Time-Line Follow-Back (TLFB), a semi-structured interview. The original target sample size was 250 participants from 2 study sites (NYC and Miami) detect 60% reduction in primary outcome at 8 months in the ESTEEM arm with 90% power. The target sample size was revised on 2/28/18 to correct an imbalance in randomization; study participation ended after 44 months on 6/24/20 with a total of 254 participants enrolled.

4. OUTCOMES

The primary and secondary outcome measures are summarized in Table 1.

Domain	Measure (1°, 2°, 3°)	Source, Frequency, and Sample
HIV-risk behavior	Condomless anal sex (1°; 2°)	Interviewer-administered assessment at-home or in-office every 4 months. Condomless anal sex in the absence of either PrEP or known undetectable viral load of HIV+ primary partners, measured with the TLFB, a semi-structured interview. The TLFB yields past-90-day incidence of HIV risk behavior: condomless anal sex, sex while using drugs or alcohol, number of sexual partners, and preceding-week PrEP use (i.e., coverage defined as 4+ doses per week). Measured as any (binary) and number (count).
	Safe sex efficacy (2°)	Safer Sex Self-Efficacy Scale; self-report every 4 months.
	Decisional balance (2°)	Decisional Balance Scale; self-report every 4 months.
	PrEP uptake (2°)	Interviewer-administered assessment every 4 months
	STI risk (3°)	STI test results (gonorrhea; chlamydia) at 12 months
Mental health and substance use	Depression (2°)	HAMD (interviewer-administered), ODSIS (self-report), BSI (self-report) every 4 months
	Anxiety (2°)	BAI, OASIS, BSI, SIAS; self-report every 4 months
	Drug Abuse (2°)	SIP-D; self-report every 4 months
	Alcohol Abuse (2°)	AUDIT; self-report every 4 months
	Mental Health Diagnoses (2°)	MINI; interviewer-administered assessment every 4 months
Minority Stress	Suicidality (2°)	SIDAS; self-report every 4 months
	Rejection Sensitivity (2°)	RS; self-report every 4 months
	Internalized Homophobia (2°)	IHS; self-report every 4 months
	Internalized Homophobia (2°)	IAT; computer-administered every 4 months

STATISTICAL ANALYSIS PLAN

	Sexual Orientation Concealment (2°)	SOCS; self-report every 4 months
Universal Stress processes	Emotional Regulation (2°)	DERS; self-report every 4 months
	Rumination (2°)	RRS; self-report every 4 months
	Assertiveness (2°)	RAS; self-report every 4 months
	Social Support (2°)	MSPSS; self-report every 4 months
	Impulsivity (2°)	Go/No-Go; computer-administered every 4 months
	Cognitive Bias (2°)	SRET; computer-administered every 4 months

TLFB: Time-Line Follow-Back; MINI: Mini-International Neuropsychiatric Interview; HAM-D: Hamilton Rating Scale for Depression; BAI: SIP-D; AUDIT ODSIS: Overall Depression Severity and Impairment Scale; OASIS: Overall Anxiety Severity and Impairment Scale; BSI: Brief Severity Inventory; DERS: Difficulties in Emotion Regulation Scale; RRS: Rumination Response Scale; MSPSS: Multidimensional Scale of Perceived Social Support; RAS: Rathus Assertive Schedule; RS: Rejection Sensitivity; IHS: Internalized Homophobia; SOCS: Sexual Orientation Concealment; IAT: Implicit Associations Task; SRET: Self-Referential Encoding Task; SIDAS: Suicidal Ideation Attributes Scale; SIAS: Social Interaction Anxiety Scale
		

4.1 Primary Outcome

The primary outcome is condomless anal sex at 8-month time point (binary: Yes/No) in the absence of either PrEP or known undetectable viral load of HIV+ primary partners, measured with the Time-Line Follow-Back (TLFB), a semi-structured interview. The TLFB will yield past-90-day incidence of HIV risk behavior: condomless anal sex, sex while using drugs or alcohol, number of sexual partners, and preceding-week PrEP use (i.e., coverage defined as 4+ doses per week). The primary outcome is measured every 4 months (4, 8, 12 months).

4.2 Secondary Outcomes

Condomless anal sex at 12 months (binary); Condomless anal sex at 8 and 12 months (count); Depression severity, as measured using the HAMD depression severity score, ODSIS, and BSI at 8 and 12 month time points; Anxiety, as measured by the BAI, OASIS, BSI, and SIAS at 8 and 12 month time points; Drug abuse, as measured by the SIP-D at 8 and 12 month time points; Alcohol abuse, as measured using by the AUDIT at 8 and 12 month time points; Mental health, as defined by odds of no longer having at least one *DSM-5* diagnosis (e.g., depression, anxiety) that was present at baseline still be present at 8 and 12 month time points based on the MINI (binary); Suicidality as measured by SIDAS at 8 and 12 month time points (continuous); Minority stress as captured by rejection sensitivity measured using RS, internalized homophobia measured using IHS and IAT; and sexual orientation concealment measured using SOCS at 4 and 8 month time points (continuous); Universal stress processes as captured by emotional regulation as measured by DERS, rumination as defined by RRS, assertiveness as measured by RAS, social support as measured by MSPSS, cognitive bias as measured by SRET, and impulsivity measured by Go/No-Go at 4 and 8 month time points (continuous).

4.3 Tertiary Outcomes

STATISTICAL ANALYSIS PLAN

STI risk as defined by a diagnosis of gonorrhea; chlamydia) at 12 months; mental health mediators (as defined for the secondary outcomes).

5. RANDOMIZATION

5.1 Method of Randomization

Randomization occurred on the participant level. Participants were randomly assigned to receive one of the following three conditions: ESTEEM, CMHT, or VCT-only (N = 250 across both sites). We used a 2:2:1 randomization scheme such that for every two participants randomized to ESTEEM, two participants were randomized to CMHT and one participant was randomized to VCT-only. Randomization happened through a computer-generated program stratified by site, such that 150 were randomized at the NYC site (60 ESTEEM, 60 CMHT, 30 VCT-only) and 100 were randomized at the Miami site (40 ESTEEM, 40 CMHT, 20 VCT-only). On 2/28/18, we discovered a programming error in the randomization and participants were not being randomized 2:2:1. The randomization was corrected to ensure the final distribution was 2:2:1 and the sample size was increased to 254 to accommodate.

5.2 Allocation Concealment

An important consideration is allocation concealment to control for selection bias. Potential approaches include 1) randomizing after enrollment, 2) masking the recruiters, 3) standardizing the enrollment process with adequate training of screeners and recruiters, and 4) covariate adjustment in the analysis. We used approaches 1 through 3, and will employ approach 4, if necessary. Specifically, Qualtrics was initially used to randomize participants but was found to be doing so in error, using a 1:1:1 allocation, rather than the proposed 2:2:1. In February 2018, the following update was made: Team members agreed to a solution whereby the study changed the randomization scheme to correct for the previous 1:1:1 randomization and slow the rate of participant randomization to VCT. This was done through the use of a randomization strategy that would increase the probability of participants being assigned to ESTEEM and CMHT, and that by the end of the study would yield a 2:2:1 ratio. Based on the number of participants that were randomized from each site and their current allocation to treatment arms, it was determined that a 3:3:1 ratio of randomization should be used at each site to ensure the originally proposed balance of 2:2:1 be met by study's end. Further, it was recommended that participants be randomized in blocks at each site of 7 (3:3:1). This provision made sure that the each site retained the correction ratio consistently through the end of recruitment. At the time, to meet recruitment goals, 54 participants were remaining to be enrolled at the NYC site and 82 participants were remaining to be enrolled at the Miami site. As a precaution, the statistician recommended that each site complete a recruitment block of 7 regardless of targeted enrollment numbers. Using the remaining participants and the original target enrollment, it was suggested that NYC enroll *at least* 56 more participants (8*7) and Miami enroll *at least* an additional 84 participants (12*7). Using the SAS procedure 'Proc Plan,' 2 lists were generated per site using the block randomization method described. Based on the suggested allocation per site, a total of 140 participants were randomized to complete the study to provide a 2:2:1 balance. Envelopes containing the randomization codes were created numbered 1 to 140 per site. These envelopes were provided to each site with a tracking sheet (site list). Each envelope contained an assignment that matches each site list. When each participant was deemed eligible, the next envelope (in sequential order) was opened and treatment assigned. The

STATISTICAL ANALYSIS PLAN

assignment was logged in the tracking sheet at the site and that study statistician was notified of assignment. An identical tracking sheet was used by the statistician at Yale. To track the balance of the adjusted randomization moving forward, periodic 'check ins' between the sites and study statistician monitored the progress and these updates in enrollment numbers and study arm balance was provided to the DSMB.

Recruiters and assessors/interviewers were masked to treatment assignment up until the point in which they were enrolled.

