8.2 Comparability of Treatment Groups

To determine randomization effectiveness, differences in baseline demographic characteristics will be assessed between ESTEEM, CMHT, and VCT-only groups using appropriate graphical and statistical methods including summary statistics. The randomization is designed to produce balance on important covariates. If we find imbalance on key covariates, we will consider sensitivity analyses that adjust for those covariates. Study site will be included as a covariate in all analyses because randomization was stratified by study site.

STATISTICAL ANALYSIS PLAN

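### The ESTEEM:VCT-only allocation ratio moved from 1:1 to 3:1 in February 2018, but no analysis adjusts for randomisation period, leaving the gatekeeping contrast open to calendar-time confounding

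*SAP*

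**What the plan says.** SAP section 5.2 states that the Qualtrics randomiser was "found to be doing so in error, using a 1:1:1 allocation, rather than the proposed 2:2:1". At the correction, "54 participants were remaining to be enrolled at the NYC site and 82 participants were remaining to be enrolled at the Miami site". From then on "it was determined that a 3:3:1 ratio of randomization should be used at each site", in blocks of 7, with suggested minimums of 56 further men in NYC and 84 in Miami. Section 5.1 says of the outcome: "The randomization was corrected to ensure the final distribution was 2:2:1".

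On adjustment, section 8.2 says: "Study site will be included as a covariate in all analyses because randomization was stratified by study site". The other covariates named are:

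- race/ethnicity, in the method row of section 8.3.1 (the covariate row there lists site only);
- baseline number of sex acts (8.3.2);
- baseline score (8.4.2.1).

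Sections 8.4.1, 8.4.2.2 and 8.5.1 reuse the primary method. Two conditional routes exist. Section 5.2, listing covariate adjustment as approach 4, says "We used approaches 1 through 3, and will employ approach 4, if necessary". Section 8.2 says "If we find imbalance on key covariates, we will consider sensitivity analyses that adjust for those covariates". Neither names period or calendar time.

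**The concern.** When the allocation ratio changes during recruitment, enrolment period predicts treatment arm. If outcome risk also differs between the periods, an analysis that ignores period mixes the calendar effect with the treatment effect. Here ESTEEM:CMHT stayed 1:1 throughout, but VCT-only was over-represented early and under-represented late. Site adjustment does not remove this, because the ratio changed inside each site.

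ESTEEM versus VCT-only is the first test in the fixed sequence, so a false positive there also opens the ESTEEM versus CMHT test. A trend is conceivable on the documents' own terms. The SAP gives a 44-month span, the primary outcome counts condomless sex only in the absence of PrEP, and PrEP uptake is itself a listed outcome.

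**Working it through.** **Inputs.** Site targets 150 and 100 (SAP 5.1); 54 and 82 remaining at the change, then 56 and 84 suggested (5.2); retention 80% (6.2). The by-site counts after the change are the suggested ones, taken as realised because the total agrees.

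**Reproducing the plan's total.** Before: (150 − 54) + (100 − 82) = 96 + 18 = 114. After: 56 + 84 = 140. Sum: 254, as stated in section 6.2.

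**Arm by period.** After the change, 3:3:1 gives 24/24/8 in NYC and 36/36/12 in Miami (ESTEEM/CMHT/VCT-only). Two cases cover the unprinted early counts:

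| Case | Early NYC | Early Miami | Final split | Early share, ESTEEM | Early share, VCT-only | Site-adjusted gap |
|---|---|---|---|---|---|---|
| Expected under 1:1:1 | 32/32/32 | 6/6/6 | 98/98/58 | 38/98 = 39% | 38/58 = 66% | 21.6 points |
| Final split 2:2:1 | 37/37/22 | 5/5/8 | 102/102/50 | 42/102 = 41% | 30/50 = 60% | 18.7 points |

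The site-adjusted gap is the arm coefficient from a linear regression of early randomisation on arm and site. In a linear model it is also the fraction of a between-period risk change that enters the risk difference. For changes of 10/20/30 points the bias is 1.9–2.2/3.7–4.3/5.6–6.5 points.

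**Effect on the test.** Simulation with no treatment effect, 80% retention, an assumed early risk of 0.75 and an assumed fall between periods; modified Poisson model at 8 months with robust standard errors, arms plus site; 8,000 replicates (Monte Carlo standard error about 0.25 points at 5%).

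| Fall in risk (points) | 0 | 5 | 10 | 20 | 30 |
|---|---|---|---|---|---|
| Type I error %, no period, 1:1:1 case | 4.5 | 5.4 | 5.6 | 8.5 | 12.2 |
| Risk ratio | 1.00 | 0.99 | 0.97 | 0.94 | 0.90 |
| Type I error %, no period, 2:2:1 case | 5.4 | 5.8 | 6.4 | 7.8 | 9.5 |
| Risk ratio | 1.00 | 0.99 | 0.98 | 0.95 | 0.92 |

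With period added, type I error is 4.5–5.7% and the risk ratio 1.00–1.01 throughout. An early risk of 0.65 gives 4.4–10.9% without period and 4.6–5.2% with it. In a separate run from an early risk of 0.60, ESTEEM versus CMHT stayed at 4.1–5.6%.

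**Direction.** A fall in risk biases towards ESTEEM and a rise biases against it. For an assumed 20-point rise from 0.50, false results favouring ESTEEM are about 1% (nominal 2.5%) and those favouring VCT-only about 4–5%.

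**The 2:2:1 statement.** 114 men at 1:1:1 plus 140 at 3:3:1 gives 98:98:58 in expectation, not 2:2:1. Reaching 2:2:1 at each site needs about 22 or fewer VCT-only among 96 early NYC men (probability 0.02 under 1/3 allocation) and about 30 or fewer among all 114 (0.07).

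**The case against.** The strongest reply is that the threat depends on a trend nobody has reported. With no trend the planned test is valid, at 5 to 10 points the inflation is slight, and the bias is small beside the planned effect: reductions of 60% versus 15% give a risk ratio of 0.40/0.85 = 0.47 if every man is positive at baseline. On this view one sensitivity analysis is enough. The size argument stands, and it means the issue matters mainly if the true effect is null or small. It does not make period optional in principle: allocation probability depended on it, and the term costs almost nothing.

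Other points that stand:

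- If risk rose, the bias would work against an efficacy claim.
- The count and continuous models adjust for baseline values, which would absorb drift already visible at baseline. The bias for those outcomes has not been quantified.
- Section 5.2 says 3:3:1 was chosen from the arm counts at the time, which are not printed, so 2:2:1 may have been reached by chance. The expected split does not prove section 5.1 wrong.

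The conditional adjustment routes do not answer the concern. They are discretionary, and the comparability check in section 8.2 concerns baseline demographic characteristics, which need not reveal a calendar effect.

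**Conclusion.** The concern holds and should be fixed. The ratio change is documented, and no planned analysis conditions on it. About one fifth of any change in risk between periods would enter the gatekeeping contrast, even if the final split was 2:2:1. The consequence runs from none (no trend) through slight (about 6% type I error at a 10-point fall) to material (about 8–12% at 20 to 30 points).

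The trend sizes and early risks are assumptions; the documents give neither. The simulation uses a single-time-point model in place of the planned mixed model and leaves out race/ethnicity, assumed unrelated to period. The suggested by-site counts are treated as realised.

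**What to change.** Prespecify randomisation period (before or after the 2/28/18 change), within site, as a covariate or stratum in the primary model and in every other model with a VCT-only contrast. Section 8.2 already adjusts for site as a factor that governed allocation, and period now governs it too. At minimum, name a period-adjusted analysis of these contrasts as an unconditional sensitivity analysis. Report actual arm counts by site and period beside the 2:2:1 statements in sections 5.1 and 5.2.

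The cost is SAP wording and one or two model terms. With no trend, the linear-model formula gives a standard error increase of 1.2% to 1.7%, and the various reruns gave about 1 to 3%. No new data collection should be needed. Post-change assignments were logged at each site and at Yale, "updates in enrollment numbers and study arm balance was provided to the DSMB", and the early assignments are needed for any intent-to-treat analysis.

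### From the SAP's own counts, the February 2018 switch to 3:3:1 gives about 98:98:58 in expectation, not the stated 2:2:1, and the realised counts are not reported

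*SAP*

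**What the plan says.** SAP section 5.1 states "We used a 2:2:1 randomization scheme" and that "150 were randomized at the NYC site (60 ESTEEM, 60 CMHT, 30 VCT-only"), with a further 100 at Miami split 40/40/20. It then reports that a programming error was found on 2/28/18, and says: "The randomization was corrected to ensure the final distribution was 2:2:1 and the sample size was increased to 254 to accommodate".

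Section 5.2 gives the detail. The Qualtrics randomization had been "using a 1:1:1 allocation, rather than the proposed 2:2:1". From the numbers randomized at each site and their arm allocation at that time, "it was determined that a 3:3:1 ratio of randomization should be used at each site to ensure the originally proposed balance of 2:2:1 be met" at the end of the study, in blocks of 7. At that point "54 participants were remaining to be enrolled at the NYC site and 82 participants were remaining to be enrolled at the Miami site". Each site was to complete whole blocks, so New York was to add at least 56 (8 blocks) and Miami at least 84 (12 blocks). The section concludes that "a total of 140 participants were randomized to complete the study to provide a 2:2:1 balance".

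Section 6.2 gives 254 as the final sample size. It needs 80 evaluable participants in each of ESTEEM and CMHT and 40 in VCT-only, and assumes 80% retention at 8 months. Neither document gives arm counts at the correction or at the end of recruitment.

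**The concern.** The starting ratio, the numbers remaining, the corrected ratio and the final ratio are all stated, so they can be checked against one another. After 114 participants at 1:1:1, VCT-only is over-represented, and 140 more at 3:3:1 look too few to dilute it to one fifth. The problem is concentrated in New York, where most of the first-phase participants were. Miami had few, so the same ratio there would overshoot in the other direction.

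What is at stake is an accurate account of a known randomization error. The 2:2:1 ratio and the site-by-arm numbers are stated design features, and the arm sizes in section 6.2 rest on them. A report that took its description from section 5.1 would give a scheme and counts that do not follow from section 5.2.

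**Working it through.** **Inputs**
- Site targets: 150 in New York, 100 in Miami (SAP 5.1, 6.2).
- Remaining at the correction: 54 and 82 (SAP 5.2).
- First-phase allocation 1:1:1; later allocation 3:3:1 in blocks of 7 (SAP 5.2).
- Further enrolment: 56 and 84, together 140 (SAP 5.2).
- Final N: 254 (SAP 5.1, 6.2).

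**Step 1: reproduce the total.** Already randomized: 150 − 54 = 96 and 100 − 82 = 18, together 114. Then 114 + 140 = 254. This matches the SAP exactly, so the counts are being read as intended, and the minimum wording attached to 56 and 84 leaves no slack.

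**Step 2: expected arm counts.** For each site, expected count = first phase ÷ 3 + later phase × (3/7, 3/7, 1/7).

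| | First phase | Later phase | Expected final | Ratio | VCT-only share | 2:2:1 of same N |
|---|---|---|---|---|---|---|
| New York | 32:32:32 | 24:24:8 | 56:56:40 (152) | 1.4:1.4:1 | 26.3% | 60.8:60.8:30.4 |
| Miami | 6:6:6 | 36:36:12 | 42:42:18 (102) | 2.33:2.33:1 | 17.6% | 40.8:40.8:20.4 |
| Overall | 38:38:38 | 60:60:20 | 98:98:58 (254) | 1.69:1.69:1 | 22.8% | 101.6:101.6:50.8 |

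Expected VCT-only is 58 against 50.8 overall (7.2 over, 14%) and 40 against 30.4 in New York (9.6 over, 32%). Using 54 and 82 without completing the last blocks changes little: about 55:55:40 and 41:41:18.

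**Step 3: what would have reached 2:2:1.** After p participants at 1:1:1, the number x at 3:3:1 that brings VCT-only to one fifth solves p/3 + x/7 = (p + x)/5, so x = 7p/3. For p = 114, x = 266, for a final N of 380. Alternatively, over 140 participants VCT-only could receive only 50.8 − 38 = 12.8, which is a forward ratio of about 5:5:1, since (140/12.8 − 1)/2 = 4.97.

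**Step 4: could chance close the gap?** Assume that the first phase was simple 1:1:1 randomization; the SAP describes no blocking for it. The first-phase VCT-only count then has mean 38 and SD √(114 × 1/3 × 2/3) = 5.0.
- Overall: exact 2:2:1 needs 50.8 − 20 = 30.8. P(31 or fewer of 114) = 0.097. P(33 or fewer), which leaves final VCT-only no more than about 2 above target, = 0.186.
- New York: exact 2:2:1 needs 30.4 − 8 = 22.4 of 96, against 32 expected. P(22 or fewer) = 0.018.
- Miami would need 20.4 − 12 = 8.4 of 18, against 6 expected.

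**Step 5: effect on section 6.2.** At 80% retention: 98 × 0.8 = 78.4 in each of ESTEEM and CMHT, and 58 × 0.8 = 46.4 in VCT-only. With n₁n₂/(n₁ + n₂) as the measure of information:
- ESTEEM vs CMHT: 78.4/2 = 39.2, against 80/2 = 40 (2% lower).
- ESTEEM vs VCT-only: 78.4 × 46.4/124.8 = 29.1, against 80 × 40/120 = 26.7 (9% higher).

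**Step 6: conflicts that need no assumption.**
- The counts that section 5.1 says were randomized sum to 150 + 100 = 250, not 254. The block plan gives 152 and 102.
- Section 5.1 says a 2:2:1 scheme was used; section 5.2 describes 1:1:1 and then 3:3:1.
- Section 5.2 numbers the envelopes up to 140 at each site, but 140 is the two-site total (56 + 84).

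**The case against.** The strongest reply is that 32:32:32 and 6:6:6 are expectations. Section 5.2 says that 3:3:1 was chosen from the arm allocation at the time, which the team could see and the reader cannot. A reader might infer from the arithmetic that 2:2:1 was impossible, or that New York VCT-only had already passed its target so that no later ratio could help. The documents do not support either inference. Both treat an expected count as a realised one, and a chance departure under a true 1:1:1 scheme could leave both statements correct overall. This part of the objection stands, and it limits the point to what holds in expectation.

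Second, the text attaches 3:3:1 to each site, but it does not clearly promise that the correction would restore 2:2:1 within each site. The original targets were 2:2:1 by site; the goal of the correction is stated for the end of the study. The overall figure is therefore the fairer test, and it is the weaker one. This also stands.

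Third, 60/60/30 and 40/40/20 are labelled as original targets in the Study Summary and section 6.2, and 254 is given as the final number there. That makes the section 5.1 wording easy to correct, but as written it still reports targets as achieved counts.

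Fourth, a reader might infer a biased or underpowered primary comparison. Neither follows. Site is a covariate in all analyses (sections 8.2 and 8.3.1), which deals with an arm mix that differs between sites. The expected loss is about two evaluable participants in each of ESTEEM and CMHT, and the comparison tested first, ESTEEM vs VCT-only, gains. Section 5.2 also says that arm balance was tracked and reported to the DSMB.

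**Conclusion.** The point holds as a correction to how the allocation is described. On the SAP's stated inputs the expected final allocation is 98:98:58, not 101.6:101.6:50.8, with New York at 1.4:1.4:1 and Miami at 2.33:2.33:1. The result assumes that the first-phase counts follow the stated 1:1:1. The chance figures, about 10% overall and 2% for New York, further assume simple randomization. The realised split may differ, and only the randomization records can settle it. If those records show that the first phase was not run at 1:1:1, that statement is the one to correct; the documents alone do not show that it is wrong. The conflict between 250 and 254 and the mismatch in envelope numbering stand without any assumption. The effect on evaluable numbers is small and goes in both directions.

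**What to change.** - **Section 5.1:** label 60/60/30 and 40/40/20 as original targets. Replace "We used a 2:2:1 randomization scheme" with the ratios actually used: 1:1:1, then 3:3:1 after the correction.
- **Sections 5.1 and 5.2:** add one table of realised counts by site, arm and period (before and after 2/28/18), and state the ratio achieved at each site and overall. Replace the sentence "a total of 140 participants were randomized to complete the study to provide a 2:2:1 balance" accordingly. If the first phase was not 1:1:1, correct that statement.
- **Section 5.2:** make the envelope numbering agree with 56 and 84.
- **Section 6.2:** restate expected evaluable numbers from the realised counts. If the SAP's figures hold, these are about 78/78/46 at 80% retention. Note that ESTEEM and CMHT then fall marginally below the stated 80 each, while ESTEEM vs VCT-only gains.

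The cost is wording and one table. The SAP was revised on 9/14/2020, after study participation ended on 6/24/20, and section 5.2 describes tracking sheets at the sites and with the statistician for the envelope phase. First-phase counts should be available from the Qualtrics records or the arm allocations used to choose 3:3:1. No new data or participants are needed. The stated ratio and the ESTEEM and CMHT numbers may look slightly less favourable.
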